The studies will be conducted at UVA and will require IRB approval prior to the initiation of the trial. Thirty-six subjects with Type 1 Diabetes Mellitus will be needed to complete the protocol.

Based on our experience with similar studies, we estimate an expected 20-30% screen failures, dropouts, or withdrawals (7 to 10 subjects at UVA); thus we intend to set a recruiting target of 45 subjects. One pilot subject will be enrolled to test system performance. More than one subject may be admitted at one time.

Specific Aim 1 (SA1): Hypoglycemic risk, Open vs. Closed Loop (exercise)

Specific Aim 2 (SA2): Time within target range, Open vs. Closed Loop control during the day

Specific Aim 3 (SA3): Time within target range at night

Specific Aim 4 (Substudy/exploratory): Assess the effect size of Control Modules 1+3 (SSM+BRM) preventing nocturnal hypoglycemia and increasing time within target (80-140mg/dl) overnight as compared to CGM-augmented pump alone.

The testing of the three specific aims of the main study (SA1, SA2, SA3) involves different periods of time as presented in Figure 3. Thus, in addition to complete data, availability of partial data would allow testing some of the study hypotheses. As a general rule, a session will be considered useful for data analysis if the subject completes more than 80% of the active study protocol (29 out of 36 hours for the experimental session). Sessions completing less than 80% of the protocol will be rescheduled. Specifically, comparing risk and occurrence of hypoglycemia during the 5-hour periods encompassing exercise (14:00-19:00) on open- vs. closed-loop control will address SA1. Comparing the time within target range (70-180mg/dl) during the day (7:00-23:00) on open- vs. advisory control will address SA2, and comparing the time within target range (80-140mg/dl) and the risk for hypoglycemia overnight will address SA3 (Figure 2).

To determine sample size we used power analysis based on data from our previous closed-loop control studies, which showed significant reduction in hypoglycemia (due to Module 1) and increase in time within target during the day and overnight [15]. With N=36 subjects, the power for proving SA1 is 97% and the power for SA3 is similar, while the power for SA2 is lower, but sufficient - 85%. The significance level was reduced to $p=0.01$ to account for multiple comparisons.

[figure not shown]

Figure 2: Experimental vs. Control sessions

D. Study Duration

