 - Study personnel with direct subject contact are required to complete Blood borne Pathogens and Infection Control training annually.

Medical Personnel Training

All study nurses will be currently licensed RNs. All RNs that are employed by the study are oriented to the care of the T1D research subject. Certification of their skill level is supervised by the study Nurse Manager. Other medical personnel may be licensed Emergency Medical Technicians. All medical personnel who will have direct contact with the study subject have current certification in Basic Life Support including CPR and AED. Study physicians will be available during the trial.

I. STOPPING RULES

Entire study

The study will be stopped if three similar AE's occur that are deemed moderate or severe or if there is system communication failures, which may trigger revision of the system software. Additionally, the Principal Investigator, IRB-HSR, Safety Officer, or sponsor may decide to stop the trial or part of the trial at any time. In this case, the Principal Investigator will promptly inform the subjects and assure appropriate therapy and follow-up. Additionally the Principal Investigator will notify the IRB if the study is temporarily stopped. The pertinent regulatory authorities will be informed according to national regulations.

Early study stop will be documented and following information will be collected:

- Date and cause of the ending

- Description of any serious adverse event leading to the study ending

A subject who does not complete the protocol may be replaced or rescheduled. Available data will be exploited.

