In the unlikely event of a disruption in 911 phone service, the Charlottesville-UVA-Albemarle Emergency Communications Center can be reached via their non-emergency number [contact]. This number feeds into their main call area where 911 dispatchers are available 24/7.

J. ENDPOINTS

This study is an early feasibility study that will test the efficacy of DiAs - a *smart-phone-based system* compared to CGM-enhanced insulin pump treatment in an outpatient setting. Specifically, the main study will have randomized cross-over design with each patient participating in two study weeks: 1) experimental involving 5 days of data collection followed by 2 days of AAA control using insulin pump and available CGM (however, treatment based on CGM will be discouraged) and 2) Control week involving 5 days of data collection followed by 2 structured days of study at home. This series of sessions will provide data for the regulatory approval of the AAA system and for its deployment in a longer-term trial of AAA at home. In addition, the data will be used to estimate the effect size of the AAA vs. CGM-enhanced insulin pump treatment in an outpatient setting.

The *basic unit for most analyses is the glucose trace of an individual*, i.e. a time-stamped series of CGM data recorded for each person. Summary characteristics and group-level analyses are derived after the individual traces are processed to produce meaningful individual markers of average glycemia and glucose variation. The following primary endpoints will be assessed:

- Risk for hypoglycemia as measured by the Low BG Index associated with exercise (SA1);
- Time spent within 70-180 mg/dl during the day (SA2);
- Risk for hypoglycemia overnight and time spent within the target range of 80-140 mg/dl overnight (SA3).

In addition, the following secondary endpoints will be assessed:

- Extent postprandial glucose excursions during the day;
- Overall number and extent of hypoglycemic episodes;
- System reliability, including failure rates of system components, frequency analysis of lost or inaccurate CGM records, percent time of active control, and inter-device connections between DiAs and the CGM and between DiAs and the insulin pump;
- System functionality, including the DiAs GUI in terms of patient comfort with operating the system, and
- The DiAs remote monitoring by medical personnel/technicians to confirm appropriate functioning outside of the hospital setting.

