The specific aim SA4 of the Substudy is exploratory – no significant results are expected, but we will assess the effect size of Control Modules 1+3 (SSM+BRM) preventing nocturnal hypoglycemia and increasing time within target (80-140mg/dl) overnight as compared to CGM-augmented pump alone.

K. SUCCESS CRITERIA / GOAL

We hypothesize that, compared to CGM-augmented insulin pump treatment, AAA control will result in moderate effect size of approximately 0.3-0.5 in terms of:

- Prevention of hypoglycemia during and following exercise more efficiently than state-of-the-art care based on CGM and insulin pump;
- Increased time within the target range of 70-180 mg/dl during the day;
- Prevention of nocturnal hypoglycemia and increase of the time within target range (80-140mg/dl) overnight.

As a general rule, a session will be considered useful for data analysis if the subject completes more than 80% of the active study protocol (29 out of 36 hours for the experimental session). Sessions completing less than 80% of the protocol will be rescheduled.

L. STATISTICAL ANALYSIS PLAN

The testing of the three specific aims of the main study involves different periods of time as presented in Figure 2. Thus, in addition to complete data, availability of partial data would allow testing some of the study hypotheses. Measures of time within target range, risk and occurrence of hypoglycemia, glucose variability and system stability will be computed as previously described and will be accompanied by appropriate plots [20]. Repeated measures ANOVA with contrasts will be used to compare the different study periods on the basis of these measures. Specifically:

- Comparing risk and occurrence of hypoglycemia during the 5-hour periods encompassing exercise (14:00-19:00) on open- vs. closed-loop control will address SA1;
- Comparing the time within target range (70-180mg/dl) during the day (7:00-23:00) on open- vs. advisory control will address SA2, and
- Comparing the time within target range (80-140mg/dl) and the risk for hypoglycemia overnight will address SA3 (see Figure 2).

II. INFORMED CONSENT

The Pilot Consent, the Informed Consent, and the Care Partner Consent are presented in Appendix A-8.

III. PATIENT CASE REPORT FORMS

Patient Case Report Forms are presented in Appendix A-9.

IV. INVESTIGATOR AGREEMENT FORMS

Investigators Agreements Forms are presented in Appendix A-10.

V. MONITORING INFORMATION

Data and Safety Monitoring Plan

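### The only named model, a repeated measures ANOVA, omits any subject lacking a compared cell, which conflicts with the plan's promise to use partial data; a mixed model per endpoint would resolve this at little cost

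*Combined protocol and SAP*

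**What the plan says.** Section I.J (Endpoints) gives the design: "the main study will have randomized cross-over design with each patient participating in two study weeks". The primary endpoints differ by aim. SA1 uses the Low BG Index around exercise, SA2 uses time in 70-180 mg/dl by day, and SA3 uses overnight hypoglycaemia risk and time in 80-140 mg/dl.

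On analysis, section I.L states: "Repeated measures ANOVA with contrasts will be used to compare the different study periods on the basis of these measures". Three comparisons follow, one per aim, each with its own window. No missing-data rule is given, no minimum data per window is set, and nothing says whether the two nights are averaged or kept apart.

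On incomplete data, sections I.C and I.L both say that "in addition to complete data, availability of partial data would allow testing some of the study hypotheses", and section I.I says "Available data will be exploited". Sections I.C and I.K count a session as usable above 80% completion (29 of 36 hours for the experimental session) and reschedule sessions below that. Non-completers may be rescheduled or replaced (section I.I).

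On power, section I.C says "Thirty-six subjects with Type 1 Diabetes Mellitus will be needed to complete the protocol", with 45 to be recruited. It adds "With N=36 subjects, the power for proving SA1 is 97" per cent, "the power for SA2 is lower, but sufficient - 85" per cent, and "The significance level was reduced to $p=0.01$ to account for multiple comparisons".

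**The concern.** The data policy and the model point in different directions. The policy keeps a subject for whichever aims the observed windows can serve. A classical repeated measures ANOVA needs every compared cell filled and discards the subject otherwise.

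How much is discarded depends on choices that the plan leaves open:

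- Hypoglycaemia risk serves both SA1 and SA3. If it is analysed in one ANOVA across exercise and overnight windows, a subject lacking a night also leaves the SA1 contrast, although both exercise windows were observed.
- If the two nights are separate cells, losing one removes the subject from SA3 even when the other night is a complete pair.
- A subject with only one usable session contributes nothing on any reading.

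At stake are observed, randomised data. So is the choice of who enters each primary test, which would otherwise be settled after the data are seen.

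**Working it through.** **1. Can cells be missing in accepted sessions?** Active control runs from 19:00 on Day 5 to 07:00 on Day 7, which is 36 hours. The session rule requires 29, so 36 - 29 = 7 hours may be absent.

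- The exercise window, 14:00-19:00, is 5 hours. It fits inside the allowance.
- Night 2, 23:00-07:00, is 8 hours. Hour 29 after 19:00 is midnight, so a session ending then is accepted with 7 of those 8 hours missing.
- A night missing in full leaves 28/36 = 77.8% and triggers rescheduling.

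One limit applies. In the experimental session, a system stopped for more than two consecutive hours is itself a reason to end study procedures (section I.I). A wholly missing exercise window in an accepted experimental session would therefore more likely come from lost glucose records than from a stopped system. The experimental week has a back-up sensor. The plan describes none for the control week.

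**2. The plan's power figures.** They cannot be derived from the documents, because the SD, the within-subject correlation, the effect scale and the sidedness are not given. For scale, treat each aim as a paired t-test, two-sided at 0.01 (sidedness assumed): power = P(T > t(0.995, n-1)), where T is noncentral t with n-1 df and noncentrality d_z × √n. Solving at n = 36 gives d_z = 0.78 for 97% and 0.63 for 85%. Section I.K states an effect size of 0.3-0.5. Read as d_z, 0.5 gives 61.1%. The scale is not stated, so this does not prove the power figures wrong.

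**3. Illustrative cost of deletion for SA1.** Hold d_z = 0.78 and assume each cell is lost independently with probability p, inside the 36 and without rescheduling. The number of complete cases is 36 × (1-p)^k for k cells, rounded to the nearest whole subject.

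| p | SA1's own window, k=2 | exercise plus averaged nights, k=4 | exercise plus two nights, k=6 |
|---|---|---|---|
| 5% | 32.5 → 32; 94.5% | 29.3 → 29; 91.5% | 26.5 → 26; 87% |
| 10% | 29.2 → 29; 91.5% | 23.6 → 24; 83% | 19.1 → 19; 70% |

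The k=4 column also describes SA3 alone with two separate nights, if its power is taken as 97% (the plan calls it similar).

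**4. Value of one-session subjects.** With n pairs, m one-session subjects split equally between conditions, correlation r and known variances, the variance of the treatment contrast relative to pairs only is [n/(1-r)] / [n/(1-r) + m/2]. Take n = 31 (45 × 0.70 = 31.5).

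- m = 7, r = 0.7: 103.3/106.8 = 0.97, a 3% reduction.
- m = 14, r = 0.3: 44.3/51.3 = 0.86, a 14% reduction.

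The values of r and m are assumptions.

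**The case against.** The strongest reply is that the plan already intends analysis aim by aim. The three comparisons listed after the ANOVA sentence each have their own window, and the partial-data sentence makes sense only if aims are tested separately. Read so, a subject missing one aim's window stays in the others. This largely stands: the joint six-cell analysis is possible under the text but not specified, and the figure defining the study periods is not shown. It does not settle how the two nights enter SA3, and it does not keep a subject with one usable session.

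Second, power is stated for 36 completers, with 45 recruited, rescheduling below 80%, repeat sessions and possible replacement. This also stands. A reader might infer that partial data are certain to be lost and that the 97% and 85% cannot be kept. The documents do not support that: with 36 subjects complete in every window there is no loss. Nor is every aim exposed to cross-window deletion. Time in 70-180 mg/dl serves SA2 alone, so a missing night or a lost Low BG Index value does not remove a subject from SA2.

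Third, the loss figures are generous. Independent 10% loss over six cells makes 1 - 0.9^6 = 47% of subjects incomplete. The plan expects 20-30% attrition with screen failures included, and windows in a stopped session tend to be lost together, so independence overstates the damage. The 14% variance reduction also needs all 14 of the other recruits (45 - 31) to have exactly one usable session. These are upper-end illustrations.

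**Conclusion.** The point holds as an inconsistency between the data policy and the named model. Section I.L promises use of partial data and names a method that omits subjects with a missing compared cell. The 80% rule limits such gaps but does not exclude them. One-session subjects are dropped on any reading. Observed pairs are dropped only if risk is modelled jointly across windows or the nights are separate cells.

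The size is conditional. Under the assumptions shown, SA1 power could be 87% (5% loss per cell) or 70% (10%) in a six-cell joint analysis, against 94.5% and 91.5% from its own window. The gain from one-session subjects is a variance reduction of 3-14%. Neither range is a prediction, and the stated power is not shown to be wrong. The change is worth making because it is cheap and fixes the analysis sets in advance, but the expected gain is modest.

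**What to change.** In section I.L, replace the repeated measures ANOVA with one linear mixed model per primary endpoint, fitted by REML with a subject random effect. Use one record per subject, session and window, and one per night for SA3. Include every randomised subject with at least one evaluable window, set the minimum data that make a window evaluable, and say how this fits with the 80% session rule. State that a missing window affects only the aim that uses it. Keep the complete-pair analysis as a sensitivity analysis.

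The cost is SAP wording and slightly more programming, with no new data or subjects. The mixed model relies on data being missing at random. Some sessions end because of glucose thresholds (section I.I), so that assumption should be stated and the reasons for missing windows tabulated.

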All adverse events	FDA	Annually	IDE annual report

Table 3: Reporting Table

E. Definition of a Protocol Enrollment Exception

An enrollment exception is the sponsor's prospective approval for the enrollment of a research subject that fails to meet current IRB-HSR approved protocol inclusion criteria, or falls under protocol exclusion criteria. Enrollment exceptions only apply to a single individual. Such a request should be rare and justified

in terms of serving the best interests of the potential study participant. Enrollment exceptions will be evaluated by the study medical monitor prior to enrollment.

F. Definition of a Data Breach

A data breach is defined in the HITECH Act (43 USC 17932) as an unauthorized acquisition, access, or use of protected health information (PHI) that compromises the security or privacy of such information.

G. Data Collection

Identifiable endpoint data be collected/recorded in the form of source documents and will be stored on a database on a Health Systems Computing Services (HS/CS) secure managed server that is configured to store PHI. De-identified data will be stored on password-protected network.

Safety Data Oversight will be completed by the Study Medical Monitor or designee. The medical monitor's designee will be a staff member from the institutional Clinical Trials Office. Monitoring Form example presented in Appendix A-11.

The PI will conduct an aggregate review of the following data:

- All adverse events
- Unanticipated Problems
- Protocol violations
- Audit results
- Early withdrawals
- Endpoint data

Other: In addition to the above, the reports will include subject enrollment. The principal investigator will also include the results of the safety reviews in the annual progress reports submitted to the IRB.

The annual report will address:

- Whether adverse event rates are consistent with pre-study assumptions
- Reason for dropouts from the study
- Whether all subjects met entry criteria
- Whether continuation of the study is justified
- Conditions whereby the study might be terminated prematurely

The relevant device regulation for reporting adverse events to the FDA will also be followed.

Data from each subject will be reviewed by the PI after completion of participation to determine whether the DiAs system was working properly and whether there were safety concerns.

IRB-HSR will be updated annually on the IRB-HSR continuation status form.

H. Adverse Events / Unanticipated Problems

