Recording, Reporting, and Grading

Only adverse events that are deemed related AND serious will be recorded, reported, and graded. The principal investigator will be responsible for the overall safety monitoring of the study. He, along with the sub-investigators, will review the individual adverse events as they occur. Any event that merits adverse event report will be collected and recorded in the IRB database by completing the IRB Adverse Event Reporting form online. The principal investigator can then use this database to produce a report of all adverse events reported on the study to do an aggregate review. If the AE is unexpected and serious, a signed hard copy of the IRB Adverse Event Reporting form will be submitted to the IRB within 7 calendar days.

I. Grading of Adverse Events

- Mild/Moderate/Severe
- Serious/Not serious
- The PI will determine the relationship of adverse events to the study using the following scale:
 - Related: AE is clearly related to the intervention
 - Possibly related: AE may be related to the intervention
 - Unrelated: AE is clearly not related to intervention

Reporting/recording of adverse events/unanticipated problems will begin after the subject begins study drug/device placement/intervention/study-related procedure/specimen collection.

Reporting/recording of adverse events/unanticipated problems will end at the end of study drug/device/intervention/participation.

VI. INSTITUTIONAL REVIEW BOARD DESCRIPTION

Institutional Review Board description is presented in Appendix A-12.

VII. LABELING

"CAUTION-Investigational Device. Limited by Federal (or United States) law to investigational use."

The investigational device is a system comprised of FDA-Approved and investigational component devices. The intended use of the system is the regulation of blood glucose levels in Type 1 diabetes via subcutaneous continuous glucose monitoring (CGM) and subcutaneous delivery of insulin. The use of the system is strictly limited to the clinical testing of a closed-loop control algorithm in controlled outpatient conditions.

- The FDA-Approved component devices that are used without modification are:
- Dexcom Gen4® Plus, Dexcom Inc. (PMA Number P050012)
- Roche Accu-Chek Spirit Combo insulin pump (PMA Number K111353).

We certify that we have copies of all product labeling for each approved/cleared device, which are available to any end-user/healthcare provider upon request.

The investigational component devices are:

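### Section V.H records and grades only adverse events that are both related and serious, which contradicts the study stopping rule, Table 3, the PI and annual safety reviews and the V.I grading scale

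*Combined protocol and SAP*

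**What the plan says.** Section V.H (Recording, Reporting, and Grading) sets the scope of adverse event collection: "Only adverse events that are deemed related AND serious will be recorded, reported, and graded". The sentence covers recording and grading as well as reporting. V.H also says that an event meriting an AE report goes into the IRB database, and that the PI draws the aggregate review from that database.

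Other parts of the same document assume a wider scope:

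- Section I.I, Stopping Rules: "The study will be stopped if three similar AE's occur that are deemed moderate or severe".
- Section V.G: "The PI will conduct an aggregate review of the following data", and the list that follows opens with all adverse events. The annual report must also address "Whether adverse event rates are consistent with pre-study assumptions".
- Table 3, last row: "All adverse events FDA Annually IDE annual report". Other rows send all SAEs to the sponsor whatever their cause, and serious unexpected events to the FDA if related or only possibly related.
- Section V.I: the scale runs from mild to severe, separates serious from not serious, and has three levels of relationship, the last being "Unrelated: AE is clearly not related to intervention".

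The AE definition in section V.A is broad. It takes in any adverse finding associated with the study procedures and is not limited to serious or related ones.

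**The concern.** V.H makes two judgements, seriousness and relatedness, into conditions for an event to be recorded at all. The downstream provisions use those judgements, or the severity grade, as attributes of events already recorded. The only numeric AE-based stop for the whole study depends on a severity grade that V.H withholds from most kinds of event.

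The events at issue are foreseen. Table 1 in section I.I lists hypoglycemic and hyperglycemic events that end a session without becoming an SAE, and allows the session to be repeated. Events of that kind could plausibly form a run of three similar moderate AEs.

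The stake is an auditable safety record in a study whose data are meant to support regulatory approval (section I.J). An event not recorded when it happens may be hard to recover later. A relatedness judgement made before recording also cannot be checked afterwards from the AE record.

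**Working it through.** The plan states no figure on this point, so there is none to reproduce. The check is one of consistency: take each provision that uses AEs, list the events it needs, and see which of them V.H would leave out.

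| Provision | Events it needs | Left out under V.H |
|---|---|---|
| I.I, three-event stop | Similar AEs, moderate or severe | Those that are non-serious, or not judged related |
| Table 3, sponsor | Every SAE | SAEs not judged related |
| Table 3, IRB, 7 days | Internal, serious and unexpected; no relatedness condition | Those not judged related |
| Table 3, FDA, 15 days | Serious, unexpected, related or possibly related | Possibly related events, if V.H means the top level of the V.I scale only |
| Table 3, FDA, annual | Every AE | All non-serious AEs, and SAEs not judged related |
| V.G, PI review and AE rates | Every AE | The same |
| V.I, grading | Not serious, possibly related and unrelated events included | The not serious and unrelated grades can never be used |

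Two event types show the gap. A moderate or severe AE that is not serious meets the V.A definition and the wording of I.I, but V.H neither records nor grades it. An SAE judged unrelated must go to the sponsor under Table 3, but V.H does not record it. No section in the supplied text describes a separate log for either type. The only AE store named is the IRB database.

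Illustration only: how far a filter of this kind could move a three-event count. The documents give neither the rate p of a given type of moderate or severe AE per subject, nor the share s of such events that are also related and serious. Both are assumptions, shown as ranges. Take n = 36 (planned completers, section I.C), at most one event per subject, and independent subjects:

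P(at least 3) = 1 − Σ(k = 0 to 2) C(36, k) q^k (1 − q)^(36 − k)

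Here q = p if every such event is counted, and q = p × s under V.H. For p = 0.10 with all counted: 1 − (0.0225 + 0.0901 + 0.1752) = 0.712. For p = 0.10 and s = 0.25, q = 0.025 and the result is 0.061.

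| p (assumed) | All counted | s = 0.50 | s = 0.25 | s = 0.10 |
|---|---|---|---|---|
| 0.05 | 0.268 | 0.061 | 0.010 | 0.0008 |
| 0.10 | 0.712 | 0.268 | 0.061 | 0.0056 |
| 0.20 | 0.984 | 0.712 | 0.268 | 0.035 |

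At s = 0 the count is always zero. The contradiction does not depend on any of these values.

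**The case against.** The strongest reply is that safety does not rest on the AE record alone. V.H has the investigators review individual AEs as they occur, so similar events would be noticed even if not logged. Section I.I has a second trigger, "or if there is system communication failures, which may trigger revision of the system software", and adds that "the Principal Investigator, IRB-HSR, Safety Officer, or sponsor may decide to stop the trial or part of the trial at any time". Subject-level criteria in the same section act on SMBG, ketones, glucagon use and seizure. Hypoglycemia risk is a primary endpoint and the number of hypoglycemic episodes a secondary one (I.J). Section V.G gives safety oversight to a medical monitor or designee and has the PI review each subject's data. Unanticipated device effects have their own suspension and reporting rules.

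All of this stands, and it rules out some stronger readings. A reader might infer that the stopping rule, the rate review and the FDA listing cannot be carried out at all. They can, but only on the related-and-serious subset, so they are incomplete rather than impossible. A reader might infer that the safety data would be nearly empty. The glucose endpoints, withdrawals and system failures are captured elsewhere; what is missing is the graded AE listing. A reader might also infer that the investigator alone controls what is known about safety. The medical monitor, IRB, Safety Officer and sponsor all have roles.

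The case report forms (Appendix A-9) and the monitoring form (Appendix A-11) were not supplied and may hold a fuller AE log. If so, the V.H sentence would contradict them too.

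None of these safeguards yields a set of recorded events graded for severity, seriousness and relatedness, so the contradiction remains.

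**Conclusion.** V.H is wrong as written. It conflicts with section I.I, Table 3, section V.G and section V.I. Followed literally, it leaves the three-event stop, the sponsor and FDA reporting, the PI review and the AE-rate report to work from an incomplete set of events. This follows from the text and needs no assumed rate. The one open reading is whether V.H counts a possibly related event as related. On either reading, non-serious and unrelated events are lost.

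The size of the loss is unknown. The illustration shows that it could be large or modest depending on p and s, and neither is in the documents. Its all-counted column takes I.I at its word, with no seriousness or relatedness condition. The documents do not say whether the sponsor intends that scope, or whether events in the control week count, so it should not be read as the rule's intended operating characteristic.

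**What to change.** Replace the V.H sentence with one under which every event meeting the V.A definition is recorded and graded for severity, seriousness and relatedness, in both study weeks and the substudy. Reporting routes and timelines should then follow Table 3 unchanged. The related-and-serious condition should not be kept as a filter on expedited reporting, because Table 3 has no such filter: it sends unrelated SAEs to the sponsor and possibly related events to the FDA.

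The sponsor should reconcile I.I, Table 3, V.G, V.H and V.I, and state which recorded AEs count toward the three-event rule, including whether relatedness or study week matters. That scope is for the sponsor to set. The sponsor should also confirm that the case report forms and the monitoring form match the revised text.

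The cost is a short wording change and minor extra data entry. No treatment rule changes.
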